## 1 Introduction

### 1.1 Scope of document

Commercially Confidential Information

The Statistical analysis plan (SAP) describes the implementation of the statistical analysis planned in the protocol.

### 1.2 Study reference documentation

The final study protocol (v01) dated 04 March 2021 and the final SOM (v02) dated 10 March 2021 are available at the time of the finalization of the Statistical Analysis Plan.

### 1.3 Study objectives

Objective(s)	Endpoint(s)
Primary objective(s)	Endpoint(s) for primary objective(s)

• To assess the efficacy of LNP023 compared with rituximab

	

• Ratio between baseline UPCR and UPCR at 24 weeks of treatment (from 24h urine collection)

Secondary objective(s)	Endpoint(s) for secondary objective(s)

• To assess the safety and tolerability of LNP023

	

• ECG parameters, vital signs, safety laboratory data, physical exam and collection of AEs assessed from baseline until the end of the study visit.

Commercially Confidential Information	

• Plasma levels of Bb and sC5b-9

• UPCR measured in first morning void

• Non-compartmental PK parameters related to drug exposure

• To assess the effect of LNP023 compared with rituximab on proteinuria remission and renal function

	

• Proportion of subjects with a complete remission, defined as proteinuria <math>\leq 0.3</math> g/day at 24 weeks of treatment, derived from 24h urine collection

• Proportion of subjects with a partial remission, defined as reduction of proteinuria from baseline <math>\geq 50\%</math> plus final UP <math>\leq 3.5</math> g/24h but <math>> 0.3</math> g/24h at 24 weeks of treatment, derived from 24h urine collection.

• Change in eGFR applying the Chronic Kidney Disease Epidemiology Collaboration (CKD-EPI) equation from baseline to 24 weeks of treatment

Objective(s)	Endpoint(s)

• To assess the pharmacokinetics of LNP023

	

• Plasma: non-compartmental PK parameters in plasma related to total parent drug, including, but not limited, to Tmax, Cmax, AUClast and AUCltau will be calculated for each dose level.

• Urine: renal plasma clearance derived from 24h urine at week 16.

Exploratory objective(s)	Endpoint(s) for exploratory objective(s)

Commercially Confidential Information

## 1.4 Study design and treatment

This is a randomized, open-label, two arm, parallel group, proof-of-concept, non-confirmatory study evaluating the efficacy and safety of LNP023 compared with rituximab in subjects with MN at high risk of disease progression defined on the basis of anti-PLA2R antibody titer ( $\geq 60$  RU/mL) and proteinuria ( $\geq 3.5$  g/24h).

Approximately 52 subjects will be randomized into the study: approximately 24 on LNP023 200 mg, approximately 24 on rituximab      Commercially Confidential Information

Treatment with LNP023 or rituximab is open label.

Commercially Confidential Information

Efficacy will be evaluated at the end of the 24-week period.

The randomization ratio is 1:1 (LNP023:rituximab).

Commercially Confidential Information

Proteinuria will be assessed by collecting 24h urine samples and measuring the protein to creatinine ratio (UPCR). The 24h urine samples will be collected by the subject at home on the morning of the day prior to the indicated study visit and brought to the study site on the day of visit. Samples will be collected 1) at run-in, 2) for baseline, 3) between Day 112 and Day 113, and 4) between Day 168 and Day 169 (end of treatment).

First morning void samples for monitoring UPCR and other urine parameters will be collected 11 times by the subject at home: 1 time at run-in, 1 time for baseline, 7 times during the treatment period and 2 times during safety follow-up.

Total study duration from screening until end of study (EOS) is approximately 65 weeks.

The study includes    Commercially Confidential Information

- a screening visit
- a run-in period of up to 12 weeks
- a baseline visit
- Day 1 (day of first study drug administration)
- a treatment period of 24 weeks
- a follow-up period without any treatment of 29 weeks, including the EOS visit

Commercially Confidential Information

Subjects will be randomized on Day 1 or up to 4 days before, only after eligibility is confirmed, to LNP023 or rituximab.

**Treatment period (subjects randomized to the LNP023 treatment arm)**

Treatment period lasts for 24 weeks from Day 1 to Day 169:

Commercially Confidential Information

**Treatment period (subjects randomized to the rituximab treatment arm)**

- Day 1 and Day 15: a dose of rituximab 1 g by intravenous infusion (i.v.), will be administered.

- Treatment period will continue until Day 169 without any further rituximab administration.

## **2      First interpretable results (FIR)**

Commercially Confidential Information

## **3      Interim analyses**

Commercially Confidential Information

## **4      Statistical methods: Analysis sets**

For subjects for which the actual treatment received does not match the randomized treatment the treatment actually received will be used for the analysis.

The safety analysis set will include all subjects who received any study drug.

The PK analysis set will include all subjects with at least one available valid (i.e. not flagged for exclusion) PK concentration measurement, who received any LNP023 and experienced no protocol deviations with relevant impact on PK data.

The PD analysis set will include all subjects who received any study drug and experienced no protocol deviations with relevant impact on PD/efficacy data.

The analysis sets and protocol deviation codes are related as follows:

**Table 4-1 Protocol deviation codes and analysis sets**

Category	Text description of deviation	Data exclusion
Deviation code		
	Subjects are excluded from Safety analysis in case of these PDs:	Exclude subject Safety analysis sets
INCL01	Written informed consent not obtained before any study assessment is performed.	
	Subjects are excluded from PK analysis in case of these PDs:	Exclude subject from PK analysis set
INCL01	Written informed consent not obtained before any study assessment is performed.	
	Subjects are excluded from PD analysis in case of these PDs:	Exclude subject from PD analysis set
INCL01	Written informed consent not obtained before any study assessment is performed.	

If updates to this table are needed, an amendment to the SAP needs to be implemented prior to DBL.

Commercially Confidential Information

Unless otherwise stated, throughout this document:

- *Treatment* and *treatment group* refer to the following treatment arms that will be used as labels for all outputs reported by treatment/treatment group:

○ Commercially Confidential Information

○ LNP023 200 mg b.i.d.\*

○ Rituximab 1 g i.v.

Commercially Confidential Information

Comercially Confidential Information

## 5 Statistical methods for Pharmacokinetic (PK) parameters

All subjects within the PK analysis set will be included in the PK data analysis.

### 5.1 Variables

The following pharmacokinetic parameters of LNP023 will be determined, as feasible, using the actual recorded sampling times and non-compartmental analysis method(s):

- Plasma:  $C_{max}$ ,  $T_{max}$ ,  $AUC_{last}$ ,  $AUC_{tau}$ ,  $C_{trough}$  ( $C_{min}$ ) and, if applicable  $AUC_{inf}$  and  $T1/2$ , at day 29 and day 113
- Urine:  $U_e$  (amount of LNP023 excreted in the urine), renal clearance (Clr) of LNP023 calculated from the amount excreted over 24h and percent recovery of LNP023 at day 113

Other pharmacokinetic parameters may be calculated as appropriate.

### 5.2 Descriptive analyses

Descriptive summary statistics for LNP023 plasma and urine concentration data will be provided by dose and visit/sampling timepoint, Comercially Confidential Information

Summary statistics will include n, mean (arithmetic and geometric), SD, CV (arithmetic and geometric), median, minimum, and maximum. An exception to this is  $T_{max}$  where median, minimum and maximum will be presented. Comercially Confidential Information

A geometric mean will not be reported if the dataset includes zero values.

Pharmacokinetic parameters will be listed by treatment, visit/sampling timepoint, and subject and summarized by dose with descriptive summary statistics as described above.

#### 5.2.1 Graphical presentation of results

All individual plasma concentration-time profiles for LNP023 concentration with median will be displayed graphically by treatment on linear and/or semi-log view. In addition, the mean (+/- SD) and geometric mean plasma concentration-time profiles for LNP023 by dose over time will be displayed graphically on linear and/or semi-log view.

## **6 Statistical methods for Pharmacodynamic (PD) parameters**

All subjects within the PD analysis set      Commercially Confidential Information  
will be included in the PD data analysis.

Unless otherwise stated, summary statistics of continuous data will include n, mean (arithmetic and geometric), SD, CV (arithmetic and geometric), median, minimum and maximum, as appropriate, while categorical data will be summarized as frequencies and percentages.

### **6.1 Primary objective**

The primary objective of this study is to assess the efficacy of the LNP023 200 mg compared with rituximab.

The primary aim of the study is to assess the reduction in UPCR (measured in 24h urine) in LNP023 200 mg treated subjects compared with rituximab treated subjects after 24 weeks of treatment.

In the LNP023 treatment groups subjects are considered as under treatment whilst taking the treatment and until 30 days after the last administration. In the Rituximab arm, subjects are considered as under treatment 6 months from the second infusion. Subjects who received a single Rituximab infusion are considered under treatment until 3 months after this single infusion.

#### **6.1.1 Variable**

The primary endpoint of this study is the ratio of UPCR after 24 weeks of treatment (Day 169) to baseline UPCR measured in 24h urine ( $UPCR_{24\text{weeks}}/UPCR_{\text{baseline}}$ ). Baseline is defined as the last non-missing measurement prior to randomization. This endpoint will be log-transformed prior to analysis, as it is assumed to follow a log-normal distribution.

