Pharmacokinetic assessments	
Non-compartmental parameters in plasma related to total parent drug, including, but not limited, to Tmax, Cmax, AUClast and AUCltau will be calculated for each dose level.
 
Urine: renal plasma clearance derived from 24h urine at week 16.

Key safety assessments	ECG, vital signs, safety laboratory data, physical exam and collection of AEs assessed from baseline until the end of study visit.
Other assessments	Commercially Confidential Information
Data analysis	
The primary aim of the study is to assess the reduction in UPCR (measured in 24h urine) in LNP023 treated subjects compared with subjects treated with rituximab after 24 weeks of treatment.
 
To assess the primary objective, UPCR (log-transformed ratio of UPCR at week 24 vs baseline) will be analyzed using a mixed model for repeated measures. The results will be back transformed and presented on the original scale.
 
The model will include treatment group (LNP023 200 mg, rituximab), timepoint (as study day relative to start of study treatment, i.e. Day 113 and Day 169)
 
Commercially Confidential Information
 
Baseline is defined to be the last measurement prior to first dosing. Treatment group by timepoint and timepoint by baseline will be included as interaction terms. Timepoint will be included as a repeated factor with an unstructured covariance matrix to allow adjustment for correlations between timepoints within patients. The intercurrent event considered for this analysis is early treatment discontinuation. For this intercurrent event, data from subjects who have discontinued treatment early will be regarded as missing after the discontinuation.
 
The difference between LNP023 200 mg and rituximab in change from baseline in log-transformed UPCR will be estimated from the model and presented with 95% confidence intervals. Simpler models will also be considered in case the pre-specified model does not fit the data well.
 
The following two criteria will be used to assess treatment efficacy:
 
• Statistically significant decrease (no worse than 55% increase) in UPCR at week 24 visit in LNP023 200 mg -treated subjects vs. rituximab-treated subjects at one-sided 10% level (i.e. $H_0 = (\text{ratio from BL in UPCR_LNP}) / (\text{ratio from BL in UPCR_Ritux}) \geq 1.55$)

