6.3.2 Treatment assignment, randomization

Upon signing the informed consent form by the subject, the investigator or his/her staff will contact the IRT and provide the requested identifying information to register a subject into the IRT.

A subject randomization list will be produced by the IRT provider using a validated system that automates the random assignment of subject numbers to randomization numbers. These randomization numbers are linked to the different treatment arms, which in turn are linked to medication numbers. A separate medication list will be produced by or under the responsibility of Novartis Global Clinical Supply (GCS) using a validated system that automates the random assignment of medication numbers to packs containing the study treatment.

Randomization will occur on Day 1 or up to 4 days before, after eligibility is confirmed.

Commercially Confidential Information

The randomization scheme for subjects will be reviewed and approved by a member of the Randomization Office.

Follow the details outlined in the Site Operations Manual regarding the process and timing of treatment assignment and randomization of subjects.

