Body Height	X																			
Body Weight	X			X	X		X	X							X	X	X			
Tuberculosis status	X																			
Hematology	X			X	X		X	X							X	X	X			
Urinalysis	X			X	X ⁷		X ⁷	X ⁷							X ⁷	X ⁷	X ⁷			
Clinical Chemistry	X			X	X		X	X							X	X	X			
CCI	X			X	X		X	X							X	X	X			
Electrocardiogram (ECG)	X			X	X	X	X	X							X	X	X			
24h urine collection ⁸		X		X													X			
First morning void		X ⁹		X ⁹			X	X							X	X	X ⁹			
CCI				X				X ⁷									X ⁷			
Estimated glomerular filtration rate	X			X	X		X	X							X	X	X			
CCI				X			X	X							X	X	X			

Period	Screening				Treatment															
	Visit Name	Screening	Run-in	Baseline ¹⁵	Day 1	Day 15	Day 29						Day 57	Day 85	Day 113					
Days	-83 to -76	-82 to -75	-40 to -30	-15 to -10	1	15 ±2	29 ±2						57 ±3	85 ±3	113 ±3					
Weeks of treatment	-12 to -11	-12 to -11	-6 to -5	-3 to -2	0	2	4						8	12	16					
Time (post-dose)	-	-	-	-	Pre-dose ¹	1 h	Pre-dose ¹	Pre-dose ¹	0.25 h	0.5 h	1 h	2 h	4 h	6 h	Pre-dose ¹	Pre-dose ¹	Pre-dose ¹	0.25 h	0.5 h	1h
Anti-PLA2R ¹¹	X			X			X													
PK blood collection ¹²						X	X	X	X	X	X	X	X	X		X	X	X	X	
CCI				X		X	X						X	X		X				
Complement biomarkers in plasma				X		X	X						X	X		X				
CCI					X															
Randomization					X ¹³															
Study drug administration (LNP023) ¹⁴															b.i.d.					
CCI					X		X						X	X	X					
Patient diary													X							
CCI				X		X	X						X		X		X			
CCI				X		X	X						X		X					

Period	Treatment				Post-Treatment Follow-Up		
	Visit Name	Day 113	Day 141	Day 169	Safety follow-up call	Day 266	EOS
Days	113 ±3	141 ±3		169 ±3	199 ±3	266 ±3	378 ±5
Weeks of treatment	16		20		24	28	37
Time (post-dose)	2h	4h	6h	Pre-dose ¹	Pre-dose ¹	-	-
Informed consent ²							
CCI							
Inclusion / Exclusion criteria							
Vaccination							
Renal biopsy ⁵							
Medical history/current medical conditions							
Pregnancy and assessments of fertility ⁶			S	S		S	S
Hepatitis and HIV Screen							
Demography							
Pulse rate	X		X	X		X	X
Blood Pressure	X		X	X		X	X
Body Temperature			X	X		X	X
Physical Examination				S		S	S
Body Height							
Body Weight			X	X		X	X
Tuberculosis status							
Hematology			X	X		X	X
Urinalysis			X ⁷	X ⁷		X	X
Clinical Chemistry			X	X		X	X
CCI			X	X		X	X
Electrocardiogram (ECG)	X		X	X			X

Period	Treatment				Post-Treatment Follow-Up		
Visit Name	Day 113	Day 141	Day 169		Safety follow-up call	Day 266	EOS
Days	113 ±3	141 ±3	169 ±3		199 ±3	266 ±3	378 ±5
Weeks of treatment	16		20		24	28	37

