### **6.2 Secondary objectives**

#### **6.2.1 Variables**

The variables supporting the secondary objectives are:

- Ratio of post-baseline UPCR to baseline UPCR measured in first morning void
- Complete remission (defined as proteinuria  $\leq 0.3 \text{ g/day}$  at 24 weeks of treatment, derived from 24h urine collection)
- Partial remission (defined as reduction of proteinuria from baseline  $\geq 50\%$  plus final UP  $\leq 3.5 \text{ g/24h}$  but  $> 0.3 \text{ g/24h}$  at 24 weeks of treatment, derived from 24h urine collection)

- Change in eGFR applying the Chronic Kidney Disease Epidemiology Collaboration (CKD-EPI) equation from baseline to 24 weeks of treatment
- Plasma levels of Bb and sC5b-9 biomarkers

Analysis details for these biomarkers are given in Biomarker [Section 8](#).

Baseline is defined to be the last non-missing measurement prior to randomization.

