## **7 Statistical methods for safety and tolerability data**

For all safety analyses, the safety analysis set will be used. All tables will be presented by treatment group. Baseline is defined as the last non-missing measurement prior to randomization.

Safety summaries (tables, figures) will include only data from the on-treatment period with the exception of baseline data which will also be summarized where appropriate (e.g. change from baseline summaries).

The on-treatment period in the LNP023 treatment groups lasts from the date of first administration of study treatment to 30 days after the date of the last actual administration of any study treatment. The on-treatment period in the rituximab treatment group lasts from the first administration to 6 months after the date of the second administration. Subjects who received a single rituximab infusion are considered under treatment until 3 months after this single infusion.

Summary statistics of continuous data will include n, mean, SD, median, minimum and maximum, while categorical data will be summarized as frequencies and percentages.

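### The SAP takes baseline before randomization rather than before first dose, so Day 1 pre-dose eGFR and safety values can lose baseline status and, read literally in the LNP023 arm, count as on-treatment (minor)

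*SAP*

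**What the plan says.** SAP 6.2.1, which covers the eGFR endpoint, states: "Baseline is defined to be the last non-missing measurement prior to randomization". SAP 7, which covers laboratory, ECG and vital-sign data, uses the sentence that also stands in SAP 6.1.1 and SAP 8: "Baseline is defined as the last non-missing measurement prior to randomization".

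The protocol's visible definition is in the Data analysis part of the protocol summary, within the description of the UPCR model: "Baseline is defined to be the last measurement prior to first dosing".

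The two reference points need not coincide. Protocol 6.3.2 says: "Randomization will occur on Day 1 or up to 4 days before, after eligibility is confirmed". SAP 1.4 agrees: "Subjects will be randomized on Day 1 or up to 4 days before, only after eligibility is confirmed".

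SAP 7 says that the LNP023 on-treatment period "lasts from the date of first administration of study treatment to 30 days after the date of the last actual administration". For rituximab the same section starts the period at the first administration, without the word date. Protocol 12.5.2 has the same difference between arms. SAP 7.2 builds the laboratory shift tables from baseline and the worst on-treatment value.

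**The concern.** A baseline for a treatment effect or a safety shift is normally the last value before exposure. Here the SAP can pass over a value taken just before the first dose in favor of one about two weeks older. Whether it does so depends on when randomization was carried out, which has no clinical meaning.

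The Day 1 value that is passed over still has to be placed somewhere. If the on-treatment period begins on the calendar date of the first dose, a sample drawn that morning before any drug falls inside it. An abnormality that was present before treatment could then be tabulated as having arisen on treatment.

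At stake are the summary of eGFR change to Week 24 (a secondary endpoint) and the change-from-baseline and shift summaries for safety data.

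**Working it through.** No power or sample-size figure enters this point. The check sets the definitions against the visit schedules.

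**Inputs**
- Randomization window: Day 1 or up to 4 days before (Protocol 6.3.2, SAP 1.4).
- Baseline visit: Day -15 to Day -10 in Protocol Tables 8-1 and 8-2. It may be extended while anti-PLA2R results are awaited.
- Marked at both the Baseline visit and Day 1 pre-dose, in both arms: eGFR, hematology, clinical chemistry, urinalysis, ECG, pulse, blood pressure, body temperature and weight.
- No Day 1 pre-dose mark: 24h urine, first morning void, plasma complement biomarkers.

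The tables were read from PDF, so the column positions should be confirmed against the original pages.

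**Step 1: which value becomes baseline for eGFR, laboratory tests, ECG and vital signs**

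| Randomized | Cut-off at first dosing | Cut-off at randomization (SAP) |
|---|---|---|
| Before Day 1 | Day 1 pre-dose | Baseline visit |
| Day 1, before the assessments | Day 1 pre-dose | Baseline visit |
| Day 1, after the assessments | Day 1 pre-dose | Day 1 pre-dose |

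The order of randomization and sampling on Day 1 is not stated, so the second and third rows are both possible.

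**Step 2: age of the SAP baseline in the first two rows.** With no Day 0, Day -10 and Day -15 lie 10 and 15 days before Day 1. With a Day 0, the intervals are 1 - (-10) = 11 and 1 - (-15) = 16 days. An extended baseline period makes them longer.

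**Step 3: number affected.** The documents do not give it. The range is 0 to about 52, the planned total.

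**Step 4: effect on eGFR change.** Write W for the Week 24 value, B for the Baseline-visit value and D for the Day 1 value. The two definitions differ by (W - B) - (W - D) = D - B for each subject. Protocol 1.2 gives a decline of about 5 mL/min/1.73 m² per year at albuminuria of 5 g/24h or more. As a rough guide, the average drift over the gap is 5 × 10/365 = 0.14 to 5 × 16/365 = 0.22 mL/min/1.73 m². That is small, and the randomization window is the same in both arms. Individual values of D - B will vary more, but the documents give no within-subject variability.

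**Step 5: effect on a laboratory shift table.** Suppose an LNP023 subject is randomized before Day 1. An analyte is normal at the Baseline visit, high on Day 1 pre-dose and normal at every later visit.
- Baseline before first dosing, pre-dose values excluded from the on-treatment period: high to normal.
- SAP baseline, on-treatment period taken by date: normal to high, although the high value preceded any drug.
- Same pattern in the rituximab arm, with the period starting at the administration itself: normal to normal, because the high value belongs to neither.

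**Step 6: primary endpoint.** 24h urine is collected at run-in, at baseline, between Days 112 and 113, and between Days 168 and 169. No sample is scheduled between randomization and first dose, so both definitions select the same baseline sample. The same holds for first morning void UPCR and plasma Bb and sC5b-9.

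**The case against.** **The protocol sentence belongs to the UPCR model.** Where the two definitions conflict explicitly, they select the same sample. Protocol 12.5.1 and 12.5.2 speak of baseline for eGFR and safety without defining it. This stands. A reader might infer that the SAP breaches a protocol rule for these variables; the visible text does not support that. Carrying the protocol definition over to them is reasonable, since it is the only one visible and the schedules count time from first administration, but it is not explicit.

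**A pre-randomization baseline has a rationale in an open-label trial.** It guarantees that the value was obtained before allocation was known. This is a real merit, but the visible SAP does not give it as a reason. It matters little for laboratory measures, and the Day 1 pre-dose value would still need a rule.

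**Pre-dose samples are labelled as such.** Data are summarized by visit and time, so a programmer could exclude them. A convention may also stand in redacted text, for example after the general conventions in SAP 4 or in the SAP appendix. Both are fair, and they limit the on-treatment point to what the visible wording allows when taken literally. That literal reading applies to LNP023 only, because the rituximab period does not start by date.

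**No directional bias is shown.** This also stands. The randomization window is common to both arms. If every subject were randomized before the Day 1 assessments, the Baseline visit would serve as baseline for all.

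**Conclusion.** The point holds as a minor one. For any subject randomized before the Day 1 assessments, SAP 6.2.1 and SAP 7 replace the last pre-drug eGFR, laboratory, ECG and vital-sign values with ones 10 to 16 days older, or more if the baseline period is extended. Read literally, the LNP023 on-treatment start then lets the Day 1 pre-drug laboratory value enter the shift tables as on-treatment, and the differing rituximab wording may lead to different handling by arm.

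The effect is confined to the descriptive eGFR change and the safety summaries. Shift tables are specified for laboratory data only. It would be easy to infer that the primary result is affected, because SAP 6.1.1 carries the same definition. It is not: the baseline UPCR sample, both success criteria and the power are unchanged.

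The conclusion assumes that the schedule columns are as read, that some subjects are randomized before their Day 1 assessments, and that no redacted convention already settles the matter.

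**What to change.** - In SAP 6.2.1 and 7, define baseline as the last non-missing measurement before first study drug administration. Align 6.1.1 and 8 for consistency only; no scheduled sample changes there.
- In SAP 7, start the on-treatment period in both arms at the date and time of first administration, and state that Day 1 pre-dose values are never on-treatment. Where no clock time is recorded, use the schedule's pre-dose label.

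The safety and PD sets contain only subjects who received study drug, so a first dose exists for everyone in these analyses.

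The cost is SAP wording and matching program specifications, with no new data, visits or subjects. The downside is that a Day 1 baseline may be measured after open-label allocation is known, which matters little for laboratory measures. If the sponsor prefers the pre-randomization baseline, the SAP should give the reason, and the second change is still needed.
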